Motion Syros: A randomized, double-blind, placebo-controlled study to investigate the efficacy of tradipitant in subjects affected by motion sickness during travel

Clinical Study Protocol
Vanda Pharmaceuticals Inc. [name]
tradipitant (VLY-686)
VP-VLY-686-3401
III
141315
NCT04327661

Date: 7 November 2022 Status: Final

Name of Sponsor/Company:

Vanda Pharmaceuticals Inc.

Name of Investigational Product:

Tradipitant/VLY-686

Name of Active Ingredient:

Tradipitant/VLY-686

Title of Study: Motion Syros: A randomized, double-blind, placebo-controlled study to investigate the efficacy of tradipitant in participants affected by motion sickness during travel

Study Center(s): Approximately 10-15

Studied Period:

First participant enrolled: February 2020 Estimated study duration: Forty months Phase of Development: Phase III

Number of Participants (planned): Approximately 300 affected participants will be randomized and assigned to tradipitant 85 mg, tradipitant 170 mg, or placebo in a 1:1:1 ratio. Treatment assignments will be made according to a randomization schedule.

Diagnosis and Main Criteria for Inclusion: Adult males or females aged 18-75, inclusive, with a history of motion sickness who meet inclusion criteria.

Investigational Product, Dosage and Mode of Administration: Tradipitant 170 mg PO, tradipitant 85 mg PO, or placebo once approximately 60 minutes before entering the vehicle.

Duration of Treatment: One boat trip lasting approximately 120-300 minutes on the moving vessel.

Reference Therapy, Dosage and Mode of Administration: Placebo capsules will be provided in size and appearance identical to those containing tradipitant and will be administered orally. The 170 mg tradipitant dosage will consist of two tradipitant 85 mg capsules. The 85 mg tradipitant dosage will consist of one 85 mg tradipitant capsule and one placebo capsule. The placebo group will consist of two capsules matching in appearance to the 85 mg tradipitant capsules.

Primary Objectives:

1. To assess the effects of tradipitant 85 mg and 170 mg on the prevention of vomiting from motion sickness during vehicle travel as measured by Vomiting Assessment (VA).

Secondary Objectives:

- 1. To assess the effects of tradipitant 85 mg and 170 mg on nausea severity as measured by subjective parameter Nausea Assessment (NA).
- 2. To assess the effects of tradipitant 85 mg and 170 mg on the symptoms of motion sickness as measured by subjective parameter MSAQ.
- 3. To assess the effects of tradipitant 85 mg and 170 mg on the symptoms of motion sickness as measured by subjective parameter PGI-S.
- 4. To assess the safety and tolerability of a single oral dose of tradipitant 85 mg and 170 mg.

Overall Design: This is a randomized, double-blind, placebo-controlled trial to investigate the efficacy and safety of a single 85 mg or 170 mg oral dose of tradipitant in motion sickness affected male and female participants during vehicle travel.

The screening phase will consist of the participant taking the motion sickness eligibility questionnaire (MSEQ) to assess their susceptibility to motion sickness. Following this questionnaire, the participant will be interviewed to understand their history of motion sickness. If the participant meets pre-defined criteria as being eligible based on the motion sickness eligibility questionnaire and interview, they will proceed to the next step of a screening visit at a clinical site with a physician, and simultaneously, a lab visit for a blood draw. If the participant passes the medical visit screen and blood draw based on inclusion and exclusion criteria they will proceed to the evaluation phase.

Eligible participants will be randomized 1:1:1 to tradipitant 85 mg, 170 mg, or placebo. Eligible participants will be instructed to take tradipitant 85 mg, 170 mg, or placebo approximately 60 minutes prior to entering the boat. Boat travel will last approximately 120-300 minutes. The Vomiting Assessment (VA) and Nausea Assessment (NA) questionnaires will be completed approximately every 30 minutes of vehicle travel.

After the completion of the vehicle travel, the participant will complete the Patient Global Impression of Severity Questionnaire (PGI-S) and the Motion Sickness Assessment Questionnaire (MSAQ). All questionnaires will be submitted for analysis. Participants will then return for an EOS visit within 7 days of Visit 2.

Statistical Methods: Prevention of vomiting will be assessed by the VA, with the other questionnaires serving as secondary endpoints. The percentage of vomiting will be assessed by CMH test adjusting for the trips, and nausea severity measured by NA will be assessed by analysis of variance with the treatment group and trip as main effects. The primary efficacy analysis will be based on the ITT population.

The statistical analyses will be detailed in the statistical analysis plan.

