1. STATISTICS

1.1. Sample Size and Accrual

A sample size of 100 participants per arm (300 total) will provide around 96% power to detect a 26% difference in vomiting between tradipitant and placebo assuming 50% of participants on placebo will vomit and 24% of participants on tradipitant will vomit.

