1.2. Statistical Methods and Analysis Plan

1.2.1. General

This section describes the planned statistical analyses in general terms. A complete description of the methodology will be specified in a statistical analysis plan (SAP), which will be finalized prior to unblinding. Any changes in the statistical methods described in this protocol that occur prior to unblinding will be documented in the statistical analysis plan and will not require a protocol amendment.

Statistical hypothesis testing will be performed at two sided alpha level of 0.05 unless specified otherwise. For continuous variables, population size (N for sample size and n for available data), the mean, the standard deviation (SD), the median, the minimum and maximum values will be tabulated. For categorical variables, population size and frequencies in each category will be tabulated.

Multiplicity adjustments will be used to control study wise type I error at 5%. The details will be provided in the SAP.

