1.3. Efficacy Data Analysis

1.3.1. Primary Outcome and Methodology

The primary endpoint is the percentage of vomiting as assessed by the VA questionnaire. The primary analysis method is CMH test adjusting for trips. The primary efficacy analysis will be based on the ITT population.

As there are two active doses, the higher dose 170 mg will be tested first. Vomiting rate in the 85 mg group will only be tested if the test in 170 mg group is positive.

The statistical analyses will be detailed in the statistical analysis plan (SAP).

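### Does the primary CMH test by trip lose material power because the documents do not tie the 1:1:1 randomisation to trip?

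*Combined protocol and SAP*

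**What the plan says.** On allocation, the synopsis (Number of Participants) states: "Approximately 300 affected participants will be randomized and assigned to tradipitant 85 mg, tradipitant 170 mg, or placebo in a 1:1:1 ratio". It adds: "Treatment assignments will be made according to a randomization schedule". The synopsis's Overall Design paragraph repeats the ratio: "Eligible participants will be randomized 1:1:1 to tradipitant 85 mg, 170 mg, or placebo". None of these gives a block size or a stratification factor, or says when assignment happens relative to boarding.

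On analysis, Section 1.3.1 states: "The primary analysis method is CMH test adjusting for trips". Section 1.3.2 also puts trip in the ANOVA models for the continuous secondary endpoints. The doses are tested in sequence: "As there are two active doses, the higher dose 170 mg will be tested first", and 85 mg is tested only if 170 mg succeeds.

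On power, Section 1.1 states: "A sample size of 100 participants per arm (300 total) will provide around 96% power", "assuming 50% of participants on placebo will vomit and 24% of participants on tradipitant will vomit". It does not mention trips. Section 1.2.1 sets the level: "Statistical hypothesis testing will be performed at two sided alpha level of 0.05 unless specified otherwise". The synopsis gives each participant one boat trip. The number and size of trips are not stated.

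**The concern.** A CMH test stratified by trip compares arms only among people on the same boat. A trip that lacks one of the two compared arms contributes nothing, and an uneven trip contributes less than an even one. If the analysis is stratified by trip but the randomisation is not, some information is lost for no benefit. The stated power would then describe an unstratified comparison and not the test to be run.

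At stake is power for 170 mg and, through the gate, for 85 mg as well. Permuted blocks within trip would remove the loss without extra participants, so on its face this looks like a cheap improvement left undone.

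**Working it through.** **Inputs.** From the documents: 100 per arm, 50% and 24% vomiting, two-sided 0.05, three arms at 1:1:1, CMH by trip. Assumed: equal trips of 3 to 60 randomised participants, no dropout and, at first, no difference in risk between trips.

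**Step 1: the stated power.** For two proportions with pooled variance under the null:

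- Mean rate: (0.50 + 0.24)/2 = 0.37.
- Null standard error: √(2 × 0.37 × 0.63/100) = 0.0683.
- Alternative standard error: √((0.50 × 0.50 + 0.24 × 0.76)/100) = 0.0658.
- Power: Φ((0.26 − 1.96 × 0.0683)/0.0658) = Φ(1.92) = 97.2%.

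With a continuity correction or Fisher's exact test it is 96.1%. The stated figure therefore reproduces as an unstratified two-group power.

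**Step 2: information lost when allocation ignores trip.** A trip with n₁ and n₀ participants in the two compared arms contributes n₁n₀/(n₁+n₀). With everyone in one stratum, the maximum is 100 × 100/200 = 50. If allocation is unrelated to trip, the expected contribution given n = n₁+n₀ is (n−1)/4, against n/4 when even. Each trip thus costs about 1/4 unit. With m randomised per trip there are 300/m trips, so the loss is 75/m units, or 1.5/m of the total: 25% at m = 6, 10% at m = 15, 5% at m = 30.

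**Step 3: power from the information I.** Rewriting Step 1 in terms of I:

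Power = Φ((0.26√I − 1.96√(0.37 × 0.63))/√((0.25 + 0.1824)/2)) = Φ((0.26√I − 0.946)/0.465).

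I = 50 returns 97.2%. The last three columns are simulated CMH power for 170 mg against placebo (6,000 trials per setting; Monte Carlo error 0.2 to 0.5 points).

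| Randomised per trip | Expected I, allocation unrelated to trip | Formula power | Simulated: unrelated to trip | Simulated: blocks of 6 used in trip order | Simulated: blocked within trip |
|---|---|---|---|---|---|
| 3 | 25.0 | 77.7% | 79.1% | 88.2% | 96.9% |
| 6 | 37.5 | 91.8% | 91.4% | 97.2% | 97.0% |
| 9 (33 trips, 297 people) | 41.25 | 94.0% | 94.5% | 96.6% | 97.4% |
| 12 | 43.75 | 95.2% | 95.2% | 97.2% | 97.1% |
| 15 | 45.0 | 95.7% | 95.8% | 97.5% | 97.3% |
| 20 | 46.25 | 96.1% | 95.9% | 97.2% | 97.1% |
| 30 | 47.5 | 96.6% | 96.8% | 97.2% | 97.2% |

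Trips of 6, 12 and 30 line up exactly with blocks of six, which flatters the fifth column. Trips of 9, 15 and 20 do not line up, and they still give 96.6 to 97.5%.

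**Step 4: trips that differ in risk.** This is the situation that motivates adjusting for trip. With a trip effect of SD 1 on the logit scale and the same overall rates, unrelated allocation gives 95.4% at m = 6, 97.8% at m = 12 and 98.3% at m = 20. Blocking within trip gives 98.8% at each of these sizes.

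**Step 5: validity.** Under the null with unrelated allocation, the rejection rate was 4.8% to 5.3% for trips of 3 to 30, with and without trip effects.

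**Step 6: what re-blocking could still gain.** First enrolment was February 2020, the planned duration is forty months, and the document is dated 7 November 2022. About 33 of 40 months had passed, leaving 7/40 = 17.5%. If trips are spread evenly over time (an assumption) and allocation had ignored trip so far:

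- m = 6: I rises from 37.7 to 37.7 + 0.175 × 12.3 = 39.9, and power from 91.9% to 93.3%.
- m = 15: I rises from 45.2 to 45.2 + 0.175 × 4.8 = 46.0, and power from 95.8% to 96.1%.

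**The case for a change.** The strongest case for acting has three parts.

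First, the primary objective names both doses. The chance that both succeed falls further than the chance for 170 mg alone: with allocation unrelated to trip it is about 85.6% at trips of 6 and 92.4% at trips of 15, against about 95.0% and 95.7% when blocked within trip.

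Second, the reassurance from an ordinary blocked schedule depends on slots being used in trip order. If one central schedule in blocks of six is consumed in an enrolment order unrelated to trip, the blocks give no protection: 91.5% at trips of 6, 94.7% at 10 and 96.0% at 15. The documents plan about 10 to 15 centres and do not say how slots are used.

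Third, blocking within trip costs no participants.

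The mechanism and these figures stand. They describe an adverse combination that nothing in the documents asserts: small trips together with assignment out of trip order. The stated power is for one dose against placebo, and that comparison stays above 91% even then for trips of 6 or more. Using only two of the three arms in a pairwise test is no extra loss, because 100 per arm already counts it. Blocking within trip is also not free of drawbacks. Blocks of three among people travelling together make assignments easier to guess if any are unmasked, and no-shows would erode the balance, since the ITT set in Section 1.2.2 requires dosing and vomiting data.

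**Conclusion.** The concern does not hold as a defect in the plan. The documents leave the blocking of the schedule unstated; they do not describe a schedule that conflicts with the analysis. Even the silence is weak evidence. Sections 1.4.2 and 1.4.3 cite an appendix and a section outside the visible text, and detail is deferred to a SAP whose text is not reproduced, so randomisation details may well be recorded there.

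Followed as written, the primary test is valid whatever the allocation order. Its power is close to the stated 96% unless trips are very small and assignment ignores them: about 91 to 92% at 6 per trip, about 95.5% at 15, and within about a point of the balanced figure from 20 upwards. Only trips of about 3 would bring it near 79%. Changing the schedule this late would recover roughly 1.4 points at trips of 6 and 0.3 at trips of 15, and nothing if trips are already near balance. This is a gap in description that the trial statistician fills in the ordinary course.

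The conclusion rests on equal trip sizes, no dropout, the planned event rates and an even pace of trips. Actual trip sizes mostly below six, with assignment out of trip order, would weaken it.

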1. STATISTICS

1.1. Sample Size and Accrual

A sample size of 100 participants per arm (300 total) will provide around 96% power to detect a 26% difference in vomiting between tradipitant and placebo assuming 50% of participants on placebo will vomit and 24% of participants on tradipitant will vomit.

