1.2.2. Participant Populations for Analysis

Three participant populations will be defined:

Intent-To-Treat population (ITT population): Any participant randomized that received a dose of study drug and had post baseline VA data. ITT population are analyzed as they are randomized, regardless of which treatment a participant received.

Safety population (Safety population): Any participant randomized that received a dose of study drug. Safety population are analyzed based on the actual treatment received.

Per-Protocol population (PP population): Any participant who was randomized and received the protocol required study drug exposure and required protocol processing. Blinded clinical data will be reviewed prior to data lock to finalize the list of PP population.

The primary analyses will be performed in the intent-to-treat population. Analyses of efficacy endpoints in the PP population will provide supportive evidence. Safety summaries will be based on the Safety population.

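### Does the 96% power in section 1.1 overstate the chance of a positive 85 mg result, given that 85 mg is tested only after 170 mg succeeds?

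*Combined protocol and SAP*

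**What the plan says.** Section 1.1 (Sample Size and Accrual) gives a single power statement. With 100 participants per arm the study "will provide around 96% power to detect a 26% difference in vomiting between tradipitant and placebo". The vomiting rates behind this are 50% for placebo and 24% for active treatment. The section gives one active rate, does not say which dose it refers to, names no test, and mentions no allowance for participants who are not analysed.

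The synopsis puts both 85 mg and 170 mg in the primary objective, with equal allocation to the three arms. Section 1.3.1 (Primary Outcome and Methodology) makes the primary analysis a CMH test adjusted for trip and sets a fixed sequence that starts with the higher dose. The condition for the lower dose is explicit: "Vomiting rate in the 85 mg group will only be tested if the test in 170 mg group is positive". Section 1.2.1 (General) sets the level: "Statistical hypothesis testing will be performed at two sided alpha level of 0.05 unless specified otherwise". It leaves the details of the multiplicity control to the SAP.

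The primary analysis set in section 1.2.2 is narrower than all randomised participants: "Any participant randomized that received a dose of study drug and had post baseline VA data".

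**The concern.** The primary objective covers two doses, but the plan quotes one power, for tradipitant without a dose. Under the fixed sequence, the unconditional chance of a positive 85 mg result is the chance that both tests are significant, and this must be below the power of either test alone. A reader could credit the 85 mg claim with 96% when the plan's own testing order gives it less.

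The figure also rests on 100 analysed per arm. That equals the number to be randomised, while the primary set drops anyone without a dose or without post-baseline VA data. If the true power for 85 mg were well below 96%, the trial might be too small for half of its primary objective.

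**Working it through.** **Inputs.** From section 1.1: placebo rate 0.50, active rate 0.24, n = 100 per arm. From section 1.2.1: two-sided 0.05. From section 1.3.1: 170 mg first, then 85 mg. Assumed, because section 1.1 does not split the rate by dose: both doses have the 24% rate.

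**1. Reproduce the stated figure (one comparison).** The pooled rate is (0.50 + 0.24)/2 = 0.37.

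- Standard error under the null: √(2 × 0.37 × 0.63/100) = 0.0683.
- Standard error under the alternative: √((0.50 × 0.50 + 0.24 × 0.76)/100) = 0.0658.
- Uncorrected: Φ((0.26 − 1.96 × 0.0683)/0.0658) = Φ(1.92) = 97.2%.
- With continuity correction 1/n = 0.01: Φ((0.25 − 1.96 × 0.0683)/0.0658) = Φ(1.77) = 96.1%.

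Exact binomial enumeration gives 96.1% for Fisher's or the Yates-corrected test, and 97.2% for the unstratified, uncorrected CMH statistic. Solving the corrected formula for 96% power returns exactly 100 per arm. The stated figure is therefore sound as a per-comparison power. It probably came from a corrected calculation, though the section does not say so.

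**2. Both tests significant.** The two comparisons share the placebo arm. Given a placebo count x, they are independent and, at equal active rates, have the same rejection probability. So

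joint power = Σₓ P(x) × [P(reject | x)]².

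The results for 100 per arm, and for assumed losses of 5% and 10%, are:

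| Analysed per arm | Fisher/Yates: 170 mg | Fisher/Yates: both | CMH, no strata: 170 mg | CMH, no strata: both |
|---|---|---|---|---|
| 100 | 96.1% | 93.0% | 97.2% | 94.9% |
| 95 | 95.1% | 91.4% | 96.4% | 93.6% |
| 90 | 94.3% | 90.2% | 95.8% | 92.6% |

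As a check, a bivariate normal with correlation 0.25/(0.25 + 0.1824) = 0.578 gives 93.3% (corrected) and 95.2% (uncorrected). Treating the tests as independent would give 0.9606² = 92.3%, which is too low because the shared placebo arm links them.

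**3. Power of 85 mg once 170 mg has succeeded.** 93.03/96.06 = 96.8% (Fisher), or 94.89/97.15 = 97.7% (CMH).

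**4. What the sequence costs against an alternative.** If the 5% were split equally, each dose would be tested at two-sided 0.025. The uncorrected formula then gives 94.8% per dose. On the same approximation the fixed sequence gives 97.2% for 170 mg and 95.2% for 85 mg. At equal rates, neither dose loses power by being put in sequence.

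**5. Sensitivity to the 85 mg rate.** If 85 mg had a 30% rate (assumed), the chance that both tests succeed would be 78% (Fisher) or 82% (uncorrected chi-square). Single-comparison power at 50% versus 30% is itself 83% by the uncorrected formula. Nearly all of that fall comes from the smaller effect, and little from the sequence.

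**The case for a change.** The strongest case for a change is that the fix is one sentence. It would name the dose, the test and the number analysed, and so bring section 1.1 into line with the testing order in 1.3.1 and the analysis set in 1.2.2. The arithmetic behind that case is right: 93.0% and 94.9% are correct on their bases, and 96% is not the unconditional chance of a positive 85 mg result. It is also true that the common 24% rate is the favourable case for the lower dose and that section 1.1 does not show this dependence.

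What does not stand is the step from there to an error in the plan.

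- Section 1.1 describes a two-group difference and gives the power for it. Quoting per-comparison power under a fixed sequence is a common choice.
- The larger gap, 93% against 96%, needs a Fisher or continuity-corrected test that the plan never names. With the planned CMH statistic, ignoring strata, the joint figure is about 95%, close to what is stated.
- The power of the trip-stratified test cannot be computed, since the documents give no trip sizes or trip-specific rates. A 1 to 3 point difference is thus finer than the available inputs support.
- The losses of 5% and 10% are assumptions. The design is a single dose and one boat trip, with VA about every 30 minutes, so a dosed traveller has several chances to supply post-baseline data.

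**Conclusion.** The concern does not call for a change. The 96% is correct as the power of one comparison with 100 analysed per arm. The unconditional chance of a positive 85 mg result is lower, at about 93% (Fisher or continuity-corrected) to 95% (uncorrected CMH without trip strata). It stays above 90% with up to 10% not analysed. These figures assume that both doses share the 24% rate, and they ignore stratification by trip.

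Following the plan as written gives the same tests, the same control of the error rate, the same sample size and the same conclusions whether or not a second power figure is printed. The gap is one of reporting detail, and a reader can fill it from the plan's own inputs. Any author who later quotes a power for 85 mg should state the test, the assumed 85 mg rate, and whether the figure is unconditional or given success at 170 mg. The assumed 85 mg rate matters far more than the testing order.

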1.2. Statistical Methods and Analysis Plan

1.2.1. General

This section describes the planned statistical analyses in general terms. A complete description of the methodology will be specified in a statistical analysis plan (SAP), which will be finalized prior to unblinding. Any changes in the statistical methods described in this protocol that occur prior to unblinding will be documented in the statistical analysis plan and will not require a protocol amendment.

Statistical hypothesis testing will be performed at two sided alpha level of 0.05 unless specified otherwise. For continuous variables, population size (N for sample size and n for available data), the mean, the standard deviation (SD), the median, the minimum and maximum values will be tabulated. For categorical variables, population size and frequencies in each category will be tabulated.

Multiplicity adjustments will be used to control study wise type I error at 5%. The details will be provided in the SAP.

